9.7.4 Assessment of cases for a signal of major structural birth defects

An aggregate assessment of cases with major structural birth defects will be conducted at each interim report and for the final report for the study. This assessment will be conducted by the investigators and reviewed by the Scientific Advisory Board members. The assessment will consist of the following steps:

- 1 a review of specific birth defects for any evidence of a cluster of similar multiple malformations, or clusters of similar isolated major birth defects among exposed pregnancies that does not occur in the comparison pregnancies;
- 2 a review of alternative aetiologies for the specific birth defects clusters, such as family history or co-exposures;
- 3 a review of the biologic plausibility of the gestational timing of exposure to the medication relative to the embryologic timing of initiation of the specific birth defect(s);
- 4 a review of the cumulative published literature for any evidence consistent with the occurrence of that cluster of defects with exposure to the medication in pregnancy.

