9.5 Study size

The proposed sample sizes in each of the three study groups are as follows:

- 200 women exposed to benralizumab at any time 8 weeks prior to LMP and throughout pregnancy
- 300 women with treated asthma, unexposed to benralizumab, aiming to represent the full spectrum of asthma severity with emphasis on severe patients
- 300 non-asthmatic comparison women

The sample size is considered plausible based on the experience of the OTIS research group with previous studies of asthma in pregnancy, but enrollment rates for the current study are unknown. Although it is unknown to what extent benralizumab will be used by pregnant women, experience with recruitment in the omalizumab (Xolair) EXPECT registry provides some support for the proposed sample size. In six years of recruitment, the EXPECT registry recruited 191 exposed pregnancies ([J. Namazy et al., 2015](#)).

No formal statistical hypothesis testing will be done. Point estimates of the rate ratios and associated CI's between the benralizumab exposed cohort and the unexposed cohorts will be used to evaluate the potential risk of benralizumab to mothers and fetuses.

Table 5 is included to contextualize the magnitude of reported relative risks. This outlines the probability of observing rate ratios in excess of different thresholds either by chance (i.e., when the true underlying risk ratio is 1) or when there is a true underlying increase in risk (RR of 1.2, 1.5 or 2), given the planned sample size.

- If the truth is that there is no increase in risk (true RR=1), the current study would have a relatively small probability (<20%) of reporting out an observed relative risk of 1.5 or greater.
- If the truth is that there is a doubling of risk, the current study would have a higher probability of reporting an observed RR greater than 1.5 ($\geq 70\%$), and a smaller probability of reporting out an observed RR < 1.2 ($\leq 13\%$).

Table 5 Probability that observed relative risk point estimates (exposed/unexposed) will exceed different thresholds

Outcome	Prevalence in unexposed cohort	Expected number of Exposed/ Unexposed Asthmatic cohorts		True RR	Probability observed RR exceeds X			
		enrolled	with complete outcome		X=1.2	X=1.5	X=2.0	X=3.0
All major birth defects in live born infants	3%	200/300	180/270	1	0.38	0.19	0.10	0.02
				1.2	0.51	0.29	0.16	0.04
				1.5	0.68	0.45	0.27	0.08
				2	0.87	0.70	0.49	0.18
Preterm birth	7%	200/300	180/270	1	0.30	0.10	0.02	0.00
				1.2	0.50	0.22	0.06	0.00

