It is also possible given the limited sample size that by chance a false positive association may be detected. In this context, the review for evidence of a pattern of major structural defects, and for a pattern of adverse outcomes associated with exposure will be used to help with interpretation of results.

Strengths of the study design are the ability to build on the referral network of OTIS member services across the U.S. and Canada to identify benralizumab-exposed pregnancies as well as appropriate comparison group pregnancies, and the OTIS research group has an excellent participant retention rate (<5% lost to follow-up). In addition, the study design allows for appropriate comparison to a treated disease group, and for appropriate attention to confounding or effect modification.

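### Step 1 of the birth-defect case review looks for exposed clusters that are absent from the comparison pregnancies, so a disproportionate cluster that also appears there has no stated way in

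*Protocol*

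**What the plan says.** Protocol 9.7.4 sets out a four-step review of cases, and its timing is fixed: "An aggregate assessment of cases with major structural birth defects will be conducted at each interim report and for the final report for the study". Step 1 names two kinds of cluster. For defects that occur together it asks for "a review of specific birth defects for any evidence of a cluster of similar multiple malformations". For single defects, it adds a search for "clusters of similar isolated major birth defects among exposed pregnancies that does not occur in the comparison pregnancies". Step 2 considers other causes of the clusters found. Step 3 compares the timing of exposure with the embryology of the specific defect or defects. Step 4 searches the literature for the same cluster. Neither a cluster size nor any count, proportion or ratio is given.

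Section 9.9 gives the review a role in reading the results. It notes that a small study may produce a false positive by chance, and offers the pattern review as an aid in judging such findings: "the review for evidence of a pattern of major structural defects, and for a pattern of adverse outcomes associated with exposure will be used".

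The quantitative comparison in 9.7.1 is a relative risk for all major structural defects together, with exact 95% and 80% confidence intervals.

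**The concern.** A comparison group shows how often a defect occurs without the drug, so that an excess can be recognised. Step 1 uses it differently: a cluster is looked for among the exposed on the condition that it is not also found among the comparators. Nothing covers a cluster found in both but far more often among the exposed. Steps 2 and 4 refer back to the clusters from step 1, so such a cluster has no stated route to the review of causes or of the literature.

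Two things follow if the wording is applied literally. The review is weakest for the less rare defects, which are the ones most able to recur among about 180 exposed births. It also becomes less sensitive as comparators are added, although more comparators should make an excess easier to see. This matters because 9.7.4 is the only place where the protocol describes comparing specific defects between exposed and comparison pregnancies.

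**Working it through.** **Inputs from the protocol**
- Exposed: "200 women exposed to benralizumab at any time 8 weeks prior to LMP and throughout pregnancy" (9.5). Table 5 takes 180 with complete outcome, which is 90% of 200.
- Comparators: "300 women with treated asthma, unexposed to benralizumab" and "300 non-asthmatic comparison women" (9.5). Table 5 takes 270 of the treated asthma group.
- Overall prevalence of major defects in the asthmatic comparison group: 3% (9.5).

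**Assumptions**
- The 90% also holds for the non-asthmatic group, giving 0.9 × (300 + 300) = 540 comparator live births. Table 5 covers only the asthmatic group.
- Background prevalence q of a single defect is 0.1%, 0.2% or 0.4%. The protocol gives no such figure.
- Two similar cases make a cluster. The protocol sets no size.

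**The plan's own figures.** Section 9.7.4 states none. The nearest are in Table 5 for all major defects. Exact enumeration of two binomials (180 and 270, prevalence 3%) gives P(observed RR > 1.5) = 0.187 at true RR 1 and 0.698 at true RR 2, against 0.19 and 0.70 stated. These figures reproduce.

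**Chance that background alone puts a cluster among the comparators.** P(≥2) = 1 − (1 − q)^n − n·q·(1 − q)^(n−1). For n = 540:
- q = 0.1%: 1 − 0.583 − 0.315 = 0.102
- q = 0.2%: 1 − 0.339 − 0.367 = 0.294
- q = 0.4%: 1 − 0.115 − 0.249 = 0.636

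If only the 270 treated asthma births counted as comparators, the same formula gives 0.030, 0.102 and 0.294. Doubling the comparators therefore roughly doubles or triples the chance that a cluster falls outside step 1.

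**Example.** 4/180 against 2/540: (4/180)/(2/540) = 0.02222/0.00370 = 6.0. Both groups have at least two cases, so the cluster does occur in the comparison pregnancies and step 1 as worded does not take it up.

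**Loss when the excess is real.** The two groups are independent, so P(at least 3 exposed cases and fewer than 2 comparator cases) is a product:
- q = 0.2%, true ratio 10: 0.700 × (1 − 0.294) = 0.49
- q = 0.4%, true ratio 6: 0.809 × (1 − 0.636) = 0.29

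The exposed cluster itself appears with probability 0.70 and 0.81. The comparator clause leaves 0.49 and 0.29.

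**Does the pooled relative risk cover the gap?** Take a sixfold rise in one defect with q = 0.2%, inside the 3% total. Exposed prevalence becomes 3% + 5 × 0.2% = 4%, so the true overall ratio is 4/3 = 1.33. By the Table 5 method, P(observed RR > 1.5) is 0.36, against 0.19 with no effect. The pooled measure responds only weakly.

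**The case against.** The strongest reply is that 9.7.4 is an expert review and not a decision rule. It looks for any evidence, has no threshold and no closing step, and step 3 speaks of specific defects and not only of clusters. Competent reviewers who saw four exposed cases against two in a group three times as large would hardly ignore them.

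Other routes also exist. Major defects in exposed pregnancies go to the sponsor as serious adverse events and are assessed individually for causality, with no condition about comparators. The sponsor's signal detection is stated to be additional to 9.7.4 (both section 11). The advisory committee may ask for further analyses (12.1.2). Section 9.9 presents the pattern review as a help in reading chance positives, not as the safeguard against missed signals.

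All of this stands, and it limits the consequence. It does not supply the missing comparison: individual causality review has no comparator rates, the sponsor's surveillance is described only as routine, and a committee request depends on someone noticing the pattern. A defect-by-cohort table could be left to the statistical analysis plan, but the criterion in step 1 is fixed in the protocol.

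A reader might also infer that one comparator with the same defect is enough to dismiss a signal. The text does not support that. Grammatically it is the cluster that must be absent, so 3/180 against 1/540 (ratio 9) still meets step 1. The chance of at least one comparator case (66% in 540 at 0.2%) is therefore not the relevant figure. Nor does any sentence say that a finding is dismissed. The fault is that a disproportionate cluster is not brought in.

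**Conclusion.** The point holds as a gap in the wording of step 1. It asks for absence where it should also ask for excess, and a cluster seen in both groups but much more often among the exposed has no stated route into the review. The chance that background alone creates this situation is about 10% to 64% for an assumed single-defect prevalence of 0.1% to 0.4%. This rests on 540 comparator births and on two cases making a cluster. For a rarer defect, a larger cluster size or only the asthmatic comparators, it is smaller. The figures illustrate literal use of the wording and do not predict how reviewers would act. The change is worth making because it is cheap and because the pooled relative risk is a weak substitute for a defect-specific comparison.

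**What to change.** Reword step 1 of 9.7.4 so that the review covers clusters of similar multiple or isolated major defects that are either absent from the comparison pregnancies or present in a higher proportion of exposed than of comparison pregnancies. For each clustered defect, show the count and denominator in each cohort. Add that comparator cases alone do not end the review.

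This costs about one reworded sentence, one added sentence and one small table per report. The downside is that a few more chance clusters go on to steps 2 to 4. For example, 2/180 against 5/540 has a ratio of (2/180)/(5/540) = 1.2 and would qualify if two cases make a cluster. Those steps exist to sort such clusters out.

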9.8 Quality control

As noted in Section 9.6, quality control measures are in place throughout the entire period of data collection and data entry. Training and retraining of study staff is monitored per study Standard Operating Procedures, and validation of data entry for critical study variables is conducted for 100% of study maternal interviews. Data exported for interim reports and final

analyses for this study are checked for logical errors, and range checks are performed. All major structural birth defect classifications are verified by the study investigators. Data are reviewed on an interim basis by the VAMPSS external advisory committee (See Section 12.1.2). Final data sets are cleaned and utilized for preparation of the analyses and study reports. All analyses (coding and output) are reviewed by the OTIS Research Center lead study statistician and at least one other staff statistician. Study reports are reviewed by the Study Manager and the Investigators. All data sets and analytic files are archived indefinitely at the OTIS Research Center, and analyses can be replicated as necessary.

9.9 Limitations of the research methods

Potential limitations of the research methods include:

The study relies on a volunteer sample which may or may not be entirely representative of all women who take benralizumab during pregnancy. However, for a new product used for a relatively rare condition this is likely one of the only methods of obtaining safety information for pregnancy exposures because of the ability to target key patient and provider groups, particularly physicians who treat patients with more severe asthma, to increase awareness about the study.

It is unknown what the distribution of gestational timing of exposure will be in the benralizumab-exposed cohort. In the EXPECT registry for omalizumab, pregnancy exposures were predominately limited to the first trimester (J. Namazy et al., 2015). Therefore, it is possible that the study will only be able to address the risks or safety of exposures that occur in the first few weeks of pregnancy before women typically recognize that they are pregnant.

The sample size that is achievable for a new product used for a relatively rare condition limits the power to detect differences, especially for rare outcomes such as major structural birth defects. The study will also be limited in ability to address increased risks for spontaneous abortion as the highest risk for spontaneous abortion occurs in the gestational weeks prior to when women would typically enroll in these types of pregnancy exposure studies. However, based on expected gestational timing of enrollment, spontaneous abortion rates in late first trimester and early second trimester will be able to be addressed.

As this study does not involve matching on disease severity, it is possible that the exposed and disease-matched groups may differ on this factor. Measures of disease severity/symptom control will be captured in the study. This will allow for altering of recruitment emphasis as the study progresses to ensure that there is appropriate balance in severity between groups.

It is also possible that other exposures, as well as differences in treatment patterns among the various health care providers treating participants could be important confounders. Depending

on sample size or availability of data on these covariates, not all of these variables may be controlled in multivariable analyses.

It is also possible given the limited sample size that by chance a false positive association may be detected. In this context, the review for evidence of a pattern of major structural defects, and for a pattern of adverse outcomes associated with exposure will be used to help with interpretation of results.

Strengths of the study design are the ability to build on the referral network of OTIS member services across the U.S. and Canada to identify benralizumab-exposed pregnancies as well as appropriate comparison group pregnancies, and the OTIS research group has an excellent participant retention rate (<5% lost to follow-up). In addition, the study design allows for appropriate comparison to a treated disease group, and for appropriate attention to confounding or effect modification.

9.9.1 Study closure/un-interpretability of results

In consultation with the VAMPSS Scientific Advisory Committee, discontinuation of the study will be considered at such time as:

- Sufficient information has accumulated to meet the scientific objectives of the study
- Other methods of gathering appropriate information become achievable or are deemed preferable
- The feasibility of collecting sufficient information diminishes to unacceptable levels because of low exposure rates, poor enrollment, or losses to follow-up. Upon initiation of recruitment, the study is expected to continue to recruit for five years with recruitment ranging from 20-55 patients exposed to benralizumab per year. Regular review of enrollment numbers will be performed and numbers compared to the sponsor's data and other external data on the uptake of benralizumab to determine if uptake among women of reproductive age is consistent with enrollment rates in the cohort study. Enrollment will also be reviewed with respect to key awareness activities.
- If the Sponsor discontinues manufacturing benralizumab they may withdraw from the study upon written notification.

9.10 Other aspects

None

10. PROTECTION OF HUMAN SUBJECTS

10.1.1 Institutional Review Board / Ethics Committee

According to the FDA Guidance document, registries such as this must comply with ethical principles and regulatory requirements involving human subjects research. Therefore, this

protocol and informed consent documents must be approved by the Institutional Review Board (IRB) at the University of California, San Diego. The chairman or the recording secretary of the IRB must have signed a form indicating approval. Notification of the Board's approval of the study must be provided to the Sponsor prior to initiation of participation in the Registry.

10.1.2 Ethical conduct

This Registry will be conducted in compliance with the protocol, International Society for Pharmacoepidemiology's Guidelines for Good Epidemiology Practices for Drug, Device, and Vaccine Research in the United States, U.S. FDA regulatory requirements, in accordance with the ethical principles of the Declaration of Helsinki (1995), and the HIPAA (Health Insurance Portability and Accountability Act) ([HHS, 2002, 2003](#); [ISPE, 1996](#)).

10.1.3 Informed consent

10.1.3.1 Oral and written consent

The pregnant woman must agree to the oral consent form at the time of enrollment and before completing the intake interview. She must also sign for release of medical information and the HIPAA authorization (when applicable) to allow the study staff to obtain information on the pregnancy and the pregnancy outcome from the participant's obstetric provider, the delivery hospital, any healthcare specialist treating her indicated disease, and the infant's pediatric provider.

The original oral and signed informed consent documents, HIPAA authorizations, and medical record release forms will be stored and maintained by the OTIS Research Center. These medical record release documents are in the authorized format required by the University of California, San Diego and are compliant with HIPAA regulations.

Pregnant women under the age of 18 who are eligible for the study and who wish to participate will require written consent of their parent or guardian and written assent from themselves prior to the initial intake interview. Consent/assent forms and study participation materials are available in English or Spanish.

10.1.4 Participant confidentiality

The study makes every effort to assure participant confidentiality. Personally identifiable information is maintained in secure files with restricted access limited to only authorized personnel.

OTIS investigators, data collection and management staff reside at the MotherToBaby/OTIS Pregnancy Studies Research Center located at the University of California, San Diego. These personnel, under the supervision of the investigators, have access to the physical files and

electronic data, have documented completion of current human subjects research training, and are listed individually as authorized to have access to the study data on the study IRB-approved research plan. Final study data files used by the investigators for analysis are stripped of identifiers and archived at the OTIS Research Center without personal identifiers.

Sponsor representatives through the Scientific Advisory Committee have access to de-identified summary data as part of the periodic annual and the final study reports.

Care will be taken to ensure that no individual participant is identifiable in the data tables published in the annual interim or final reports, or other presentations or publications.

11. MANAGEMENT AND REPORTING OF ADVERSE EVENTS/ADVERSE REACTIONS

A Safety Management Plan (SMP) will be developed for the study and will provide detailed information on the study specific pharmacovigilance processes and procedures.

The purpose of the Benralizumab Pregnancy Exposure Study is to monitor planned and unplanned pregnancies exposed to benralizumab and to evaluate the possible teratogenic effect of this medication. For benralizumab-exposed pregnancies predefined specific pregnancy outcomes that are classified as serious adverse events (SAE's) will be identified and reported. These selected SAEs include major structural birth defects, spontaneous abortion, stillbirth and neonatal death, and maternal death. These events will be reported to the sponsor's safety department within 24 hours of awareness.

Tata Consultancy Services (TCS) will be responsible for processing all SAEs (as above) onto the AZ global safety database.

The following contract information should be used:

- 1 Clinical trial mailbox should be used: Clinical Trial (TCS) - [REDACTED]
- 2 The sponsor's safety department hotline for all adverse event reports is [REDACTED].
- 3 In the event of a secure email link being unavailable the following fax number should be used: Fax number [REDACTED]

If during the study, the OTIS Research Center investigators become aware of an adverse event explicitly attributed to benralizumab by the participant or her health care provider, this will also be reported to the sponsor's safety department within 24 hours of awareness. The participant will be asked if she is willing to release her contact information, or the contact information for her health care provider for follow-up by the sponsor.

Any pregnancies in women exposed to benralizumab reported to the OTIS Research Center retrospectively, or who otherwise do not meet the study eligibility criteria, will be referred to the Sponsor.

The interim and final study reports will include summary tables and analyses for each of the study endpoints as part of the research questions being addressed.

The selected SAEs of interest in this study include major structural birth defects, spontaneous abortions, elective terminations, stillbirths, neonatal deaths and maternal death in the benralizumab exposed group. The method of causality assessment of the adverse events collected in this study will include the following actions:

MotherToBaby OTIS pregnancy studies will be forwarding these SAEs to AstraZeneca for case processing and reporting within 24 hours of awareness. MotherToBaby OTIS pregnancy studies will not be providing causality assessment for the SAEs. AstraZeneca will be providing company causality assessment and will be responsible for expedited reporting. Every reported serious adverse event will undergo a formal causality assessment that will involve assessing the case as valid and reviewing each case based on medical judgement and global introspection. Using the causal criteria of temporality, biological plausibility (consistency with known drug mechanism of action and safety profile), relevance, absence of confounding factors (e.g. excluding other known human teratogens), lack of alternate etiology and consistency with current medical knowledge, each serious adverse event is reviewed by a group of senior experienced patient safety professionals. Causality of ‘related’ is made if following a review of the relevant data, there is evidence for a “reasonable possibility” of a causal relationship for the individual case. The expression “reasonable possibility” of a causal relationship is meant to convey, in general, that there are facts (evidence) or arguments to suggest a causal relationship.

Causality assessment by AstraZeneca will accompany each case reported to the regulatory agencies. An alternate aetiology or explanation will be provided in cases where causality is negative.

AstraZeneca will conduct signal detection activities as part of their routine safety surveillance processes. This is in addition to the planned analyses for each of the study endpoints conducted as part of the research questions being addressed (see section 9.7.4).

